### **8.1 Treatment Assignment**

The treatment assignment will include the cohort number and dose level in which subjects will be enrolled. The treatment assignment date is to be documented in the subject's medical record and on the enrollment eCRF.

## **9. TREATMENT PROCEDURES**

### **9.1 Classification of Product**

The Amgen investigational product used in this study is oprozomib.

The non-Amgen non-investigational products used in this study include: pomalidomide and dexamethasone.

The Investigational Product Instruction Manual (IPIM), a document external to this protocol, contains detailed information regarding the storage, preparation, destruction, and administration of oprozomib, pomalidomide and dexamethasone.

### **9.2 Investigational Product**

All investigational product(s) will be self-administered. A diary will be provided for subjects to record their adherence to the oral medication. Time of meal intake will be

recorded on subject diary for dosing days at home. For purposes of this protocol, “study treatment” refers to any combination of oprozomib, pomalidomide and dexamethasone.

### **9.2.1 Oprozomib Investigational Product**

Oprozomib will be manufactured and packaged by Amgen Inc. and distributed using Amgen clinical study drug distribution procedures. Oprozomib is formulated as:

1. Immediate release (IR) formulation: oral solid dosage form in strengths of 25 and 50 mg. Both strengths are presented as round tablets with a non-functional white film coating. The tablets will be packaged in 75 cc high-density, polyethylene bottles with desiccant and closed with heat induction seals and polypropylene child resistant closures. Each bottle will contain 30 tablets.
2. Extended release gastro-retentive (GR) formulation: oral solid dosage form in strengths of 25 mg and 100 mg. Both strengths are presented as oval tablets with a non-functional white film coating. The tablets will be packaged in 75 cc high-density, polyethylene bottles with desiccant and closed with heat induction seals and polypropylene child resistant closures. Each bottle will contain 30 tablets.

Treatment will continue until disease progression, unacceptable toxicity, or study treatment (**oprozomib**) discontinuation for any reason.

The effects of overdose of oprozomib are not known.

#### **9.2.1.2 Dose-cohort Study Escalation and Stopping Rules**

##### **Part 1**

Part 1 of the study (Od) will test a sample size of at least 3 subjects per each formulation of oprozomib. If 1 of the initial 3 evaluable subjects experiences a DLT, then 3 additional evaluable subjects will be enrolled. If 2 or more of the evaluable subjects experience a DLT (eg, 33% or higher with 6 evaluable subjects), then the dose level of 150 mg/day of that particular oprozomib formulation will be determined to be non-tolerable, and a second Part 1 cohort will be enrolled to test a decreased dose of oprozomib in combination with dexamethasone. The reduced dose of oprozomib used in subsequent cohorts will be determined based on analysis of emerging safety and PK data of the initial cohort.

After all DLT-evaluable subjects within a cohort have completed the DLT window, the DLRT will convene to review all available study data, including data collected after the initial DLT window, demographics, study treatment administration, medical history, concomitant medications, adverse events, clinical tests, vital signs, laboratory results and PK/█ information. The DLRT will make all dose and/or schedule change decisions.

##### **Part 2**

The dose escalation design will use the Bayesian 2-parameter logistic regression model, the NCRM applied to observed DLTs (Neuenschwander, 2008).

For the IR formulation, the starting dose level is 150 mg/day (2/7 schedule); the maximum and the minimum planned dose levels are 300 mg/day and 150 mg/day, respectively. Dose levels and escalation and de-escalation increments may be adjusted based on data generated in the study. One or more cohorts of at least 2 subjects may be enrolled at each dose level, depending on the toxicity observed. In accord with NCRM, the relationship between dose and the probability of DLT will be updated as additional subject safety information becomes available. After all subjects enrolled at the starting dose level are DLT-evaluable, the Bayesian Logistic Regression (BLR) model will be updated, and the NCRM will recommend the next dose level from the updated probabilities for target toxicity interval and excessive/unacceptable toxicity interval. The next cohort (eg. the Dose Level 2 or continuation of Dose Level 1) will be the dose with the highest posterior probability of having a toxicity rate in the target toxicity interval, which is defined as 15% to 25%, and will be subject to the constraint that the probability of excessive/unacceptable toxicity, which is defined as > 25% to 100%, is less than 40%. The DLRT will review the safety data and dose level recommended by the algorithm after every cohort has completed the DLT period. The DLRT will decide to expand the cohort at the current dose level, advance to the next dose level, or de-escalate to a lower dose level, based on the available data. Dose level skipping will be allowed in dose escalation decisions with a maximum increment of 50 mg/day. The NCRM will continue to assign subjects to subsequent dose levels based on the cumulative DLT data, until either the DLT rate of the recommended MTD has a probability of within the target toxicity interval (15%-25%)  $\geq$  40%, an excessive/unacceptable interval ( $>25\%-100\%$ )  $<$  40%, and a minimum of 6 subjects have been treated at the candidate MTD or the predetermined maximum sample size of 36 DLT-evaluable subjects is reached, whichever comes first.

The starting dose level of the GR formulation will be determined by the DLRT and based on the DLTs and adverse events observed in the first cohorts of the IR dose escalation and it will be at least one dose level lower than the highest dose tested of the IR formulation. This strategy will potentially reduce the sample size needed to find the MTD for the GR formulation and is currently anticipated to be 22 DLT-evaluable subjects.

The DLRT will review the available safety, efficacy and PK / [REDACTED] data and recommend a formulation and dose of OPomd for further clinical testing.

The DLRT may request additional reviews or recommend modifying or suspending the study if safety concerns arise during the study. In the event that a need to modify or

suspend the study is identified, this information will be communicated to investigators immediately.

Refer to Section 13.3.2 for additional details regarding the DLRT.

### **Dose Exploration Stopping Rules**

The DLRT may consider Part 2 dose exploration complete if one of the following rules is met:

- A total of 58 DLT-evaluable subjects have been enrolled of which 22 are anticipated for the GR formulation, or
- MTDs are identified for the IR and the GR formulations

#### **9.2.1.3 Other Rules for Holding Enrollment**

- If DLTs occur in the first 2 subjects treated with OPomd, enrollment will be held to allow DLRT review and adjustment of the algorithm.
- If there is a study drug-related Grade 5 toxicity, enrollment will be held to allow DLRT review and further decision.

The DLRT will discuss such cases to decide whether to resume enrollment.

#### **9.2.1.4 Dose Limiting Toxicities**

A DLT will be defined as any of the events described below occurring in a subject during the DLT window, and regarded by the investigators and/or Amgen medical monitor to be related to study treatment. The DLT window will be the initial 28 days of study treatment. The DLT window may be extended to assess events starting within the window in case the DLT definition is time dependent (neutropenia or thrombocytopenia, see below). Any adverse event occurring outside the DLT window that is determined by the investigator to be possibly related to the investigational product, which is seen more frequently or is more severe than expected or is persistent despite appropriate management, can be determined to be a DLT upon unanimous decision by the DLRT after review of the adverse event and all available safety data. The CTCAE version 4.03 will be used to assess the severity of toxicities/adverse events. Study drug-related is defined as a reasonable likelihood of clinical causality based on a temporal relationship, biology, de-challenge improvement and that the adverse event was not likely explained by the subject's clinical state, underlying disease, concomitant medication, or study/non-study procedure.

- Any toxicity that does not meet the criteria for DLT and requires permanent discontinuation of oprozomib treatment in cycle 1 will be considered a DLT

- A delay in ability to receive Day 1 dose of cycle 2 due to a hematologic or non-hematologic drug-related toxicity persisting beyond 14 days from cycle 1 Day 28 will be considered a DLT
- For non-hematologic toxicities, any  $\geq$  Grade 3 toxicity will be considered a DLT with exceptions as described below:
  - Grade 3 asymptomatic electrolyte abnormalities, with exception of hypophosphatemia as below, will not be considered a DLT
  - Asymptomatic Grade 3 hypophosphatemia that does not resolve within 24 hours will be considered a DLT.
  - Grade 3 nausea, vomiting and diarrhea will not be considered a DLT unless persisting longer than 3 days despite optimal supportive care (please refer to the diagram Guidelines for Oprozomib and Pomalidomide Dose Modifications and Treatments for details)
  - Grade 3 fatigue lasting  $< 14$  days is not considered a DLT
  - $\geq$  Grade 3 hyperglycemia or toxicity attributed to dexamethasone is not considered a DLT
  - $\geq$  Grade 3 rash attributed specifically to pomalidomide is not considered a DLT
- For hematologic toxicities:
  - Grade 4 neutropenia will be considered a DLT if absolute neutrophil count (ANC)  $< 0.5 \times 10^9/L$  lasting  $\geq 7$  days despite adequate growth factor support (eg., G-CSF)
  - Febrile neutropenia: any single temperature  $\geq 38.3^{\circ}C$  or a sustained temperature of  $\geq 38.0^{\circ}C$  for over 1 hour with  $\geq$  Grade 3 neutropenia (ANC  $< 1.0 \times 10^9/L$ )
  - Thrombocytopenia will be considered a DLT if:
    - Grade 4 lasting  $\geq 7$  days, or
    - Grade  $\geq 3$  with clinically significant bleeding ( $\geq$  Grade 2) or requiring platelet transfusion.
  - Grade 4 anemia is not considered a DLT

### 9.3 Non-Amgen Non-investigational Products

#### 9.3.1 Non-Amgen Non-investigational Product Pomalidomide

##### 9.3.1.1 Dosage, Administration, and Schedule

Pomalidomide is available as a capsule containing 1, 2, 3, or 4 mg of pomalidomide drug substance for oral administration. Additional product information is provided in the Pomalidomide Prescribing Information (**Pomalidomide U.S. Prescribing Information for United States; for other countries, see appropriate prescribing information**).

Pomalidomide will be administered at a dose of 4 mg on days 1 to 21 of repeated 28-day cycles. Pomalidomide may be taken with or without food. Pomalidomide may be taken with water. Subjects are to be informed not to break, chew, or open the capsules. Aspirin (or other anticoagulant or antiplatelet medication such as clopidogrel bisulfate,

low-molecular-weight heparin, or warfarin) is recommended as prophylaxis for venous and arterial thromboembolism based on assessment of the subject's underlying risk factors (refer to the Pomalidomide Prescribing Information [**Pomalidomide U.S. Prescribing Information for United States; for other countries, see appropriate prescribing information**]).

In Part 1, pomalidomide may be added to the treatment once there is a first dose level of oprozomib determined to be safe in combination with pomalidomide and dexamethasone (as determined by the first cohort in Part 2).

In Part 2, all subjects will receive pomalidomide on day 1 of cycle 1.

Subjects who permanently discontinue pomalidomide may continue on study on oprozomib and dexamethasone.

### 9.3.1.2 Dose-cohort Study Escalation and Stopping Rules

Dose reduction levels for pomalidomide are provided in [Table 3](#). Dose adjustments should, in general, follow the instructions provided in the Pomalidomide Prescribing Information 2013 (**Pomalidomide U.S. Prescribing Information for United States; for other countries, see appropriate prescribing information**). Where Pomalidomide is not available in 1 or 2 mg, sites are allowed to modify the dose of pomalidomide based on local prescribing standards.

**Table 3. Dose Decrements for Pomalidomide**

Nominal Dose	Reduced Pomalidomide Doses		
	First Dose Reduction	Second Dose Reduction	Third Dose Reduction
4 mg	3 mg	2 mg	1 mg

### 9.3.2 Non-Amgen Non-investigational Product Dexamethasone

Dexamethasone, a synthetic adrenocortical steroid, is available as tablets containing 4 or 6 mg of dexamethasone drug substance for oral administration. All subjects will receive 20 mg of dexamethasone on each oprozomib dosing day. For subjects over 75 years old, after the first cycle and at the investigator's discretion, dexamethasone can be reduced to 10 mg. It is recommended that dexamethasone be taken with food or after meals. If taken together with oprozomib IR formulation, a low fat meal is recommended. If taken together with oprozomib GR formulation, a main meal that contains the highest calorie and fat content is required. Subjects must be advised to take meals prior to dosing.

Dexamethasone may be administered intravenously (IV), if needed, at the investigator's discretion, but IV dexamethasone will not be provided by the sponsor.

### 9.3.2.1 Dose-cohort Study Escalation and Stopping Rules

Dose reduction levels for dexamethasone are provided in [Table 4](#).

**Table 4. Dose Decrements for Dexamethasone**

Nominal Dose	Reduced Dexamethasone Doses	
	First Dose Reduction	Second Dose Reduction
20 mg	12 mg	8 mg
10 mg a	8 mg	4 mg

[figure not shown]
a For subjects over 75 years old, after the first cycle and at the investigator's discretion, dexamethasone can be reduced to 10 mg

### 9.3.2.2 Dosage Adjustments, Delays, Rules for Withholding or Restarting, Permanent Discontinuation

[figure not shown]
If any dose of pomalidomide, oprozomib or dexamethasone is reduced during the previous cycle, the reduced dose level will be continued on day 1 of the next cycle. If the reduced dose level is well tolerated for a complete cycle, the subject may, at the investigator's discretion, be re-challenged with the dose level prior to the reduction at the start of the next cycle unless the subject experiences a GI hemorrhage.

In addition to dose reductions, administration of oprozomib, pomalidomide and dexamethasone may be temporarily interrupted for a maximum of 4 weeks in the event of a treatment-related toxicity. If the dose delay because of toxicity is longer than 4 weeks, the subject will be discontinued from study treatment. If a subject misses more than 4 consecutive weeks for reasons other than toxicity after completing cycle 1, the subject will be discontinued from study treatment unless it is determined that the subject was benefiting from therapy and the Amgen study medical monitor permits the subject to resume therapy.

[figure not shown]
Dexamethasone will be permanently discontinued after 2 dose reductions for either nominal dose in the event of additional dexamethasone-related toxicity. At the investigator's discretion, dexamethasone may be tapered prior to complete discontinuation according to institutional practice. If dexamethasone dosing is permanently stopped due to toxicity in accordance with the dose modification guidelines described in [Table 5](#), the subject may continue to receive oprozomib and pomalidomide, and will continue to follow protocol required therapy, procedures, and assessments. Subjects may continue to take antiemetic doses of dexamethasone (4 mg) on days of oprozomib dosing, if tolerated, at the investigator's discretion. In the event pomalidomide is permanently discontinued, oprozomib in combination with dexamethasone may be continued. Similarly, if oprozomib is discontinued, pomalidomide and dexamethasone may be continued. Please see the diagram Guidelines for Oprozomib and Pomalidomide Dose Modifications and Treatments.

[figure not shown]

a The maximum allowed dose interruption is 4 weeks for treatment-related toxicity.

[figure not shown]

a The maximum allowed dose interruption is 4 weeks for treatment-related toxicity.

a The maximum allowed dose interruption is 4 weeks for treatment-related toxicity.

a The maximum allowed dose interruption is 4 weeks for treatment-related toxicity.

b Subjects who experience Grade 1 or 2 GI hemorrhage may be re-challenged following discussion and agreement between the Amgen Medical Monitor and investigator.

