**Table 5. Guidelines for Dexamethasone-Related Toxicity**

Body System	Symptom	Recommended Action
Gastrointestinal	Dyspepsia, gastric or duodenal ulcer, or gastritis Grade 1 or 2 (requiring medical management)	Continue dexamethasone at same dose and treat with therapeutic doses of H2 blockers, or proton pump inhibitor. May consider adding sucralfate or other antiulcer treatment as clinically indicated. If symptoms persist despite above measures, decrease dexamethasone dose by 1 dose level.
	Dyspepsia, gastric or duodenal ulcer, or gastritis $\geq$ Grade 3 (requiring hospitalization or surgery)	Hold dexamethasone until symptoms return to baseline. Restart dexamethasone at 1 dose decrement along with concurrent therapy with H2 blockers, sucralfate, or omeprazole. If symptoms persist despite above measures, discontinue dexamethasone permanently.
	Acute pancreatitis	Permanently discontinue dexamethasone.
General Disorders	Edema $>$ Grade 3 ( $>$ 30% limb discrepancy in volume; gross deviation from normal anatomic contour; limiting self-care activities of daily living)	Hold dexamethasone until symptoms return to baseline. Administer diuretics as needed, and restart dexamethasone at 1 dose decrement; if edema persists despite above measures, decrease dose another level. Discontinue dexamethasone permanently if symptoms persist despite second reduction.
Psychiatric Disorders	Confusion or mood alteration $\geq$ Grade 2 (interfering with function $\pm$ interfering with activities of daily living)	Hold dexamethasone until symptoms return to baseline. Restart dexamethasone at 1 dose decrement. If symptoms persist despite above measures, reduce by another dose decrement.
Musculoskeletal	Muscle weakness $\geq$ Grade 2 (symptomatic and interfering with function $\pm$ interfering with activities of daily living)	Hold dexamethasone until symptoms return to baseline. Restart dexamethasone at 1 dose decrement. If weakness persists, decrease dose by 1 more dose level. Discontinue dexamethasone permanently if symptoms persist.

Page 1 of 2

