**Table 5. Guidelines for Dexamethasone-Related Toxicity**

Body System	Symptom	Recommended Action
Metabolism and Nutrition Disorders	Hyperglycemia $\geq$ Grade 3 (fasting glucose $> 250$ mg/dL)	Hold dexamethasone until glucose is $\leq$ Grade 2 ( $< 250$ mg/dL) and treat with insulin or other hypoglycemic agents as needed. If uncontrolled despite above measures, decrease dose by 1 dose level until $\leq$ Grade 2 ( $< 250$ mg/dL)
All Other	Other nonhematologic toxicity $\geq$ Grade 3 felt related to dexamethasone	Hold dexamethasone dose. Resume at 1 dose decrement when toxicity has resolved to Grade 2 or less or to baseline. If toxicity recurs, hold dexamethasone dose until toxicity has resolved to Grade 2 or less or to baseline and resume dexamethasone dose by 1 more dose decrements. If toxicity recurs despite 2 dose decrements, discontinue dexamethasone permanently.

Page 2 of 2

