##### **9.4.2 Gastrointestinal Toxicities**

Lansoprazole or another oral PPI is required (H2 antagonists are recommended if subject has intolerance or hypersensitivity to PPI) for the duration of treatment with oprozomib to prevent GI toxicities. In an earlier clinical study (Study 2011-001) the PK exposure of oprozomib (assessed by  $AUC_{last}$  and  $C_{max}$ ) was compared in subjects ( $n = 21$ ) receiving PPIs versus subjects ( $n=45$ ) not receiving PPIs. In this preliminary analysis, PPI did not appear to have any effect on the PK exposure of oprozomib.

Subjects who experience grade 3 or 4 GI hemorrhage during the study will not be re-challenged with oprozomib. Subjects who experience grade 1 or 2 GI hemorrhage may be re-challenged following discussion and agreement between the Amgen Medical Monitor and investigator.

It is strongly recommended that subjects be premedicated with a 5-HT3 antagonist, such as ondansetron or granisetron, prior to each dose of oprozomib and then as needed to prevent nausea and vomiting. Additional antiemetics may be used per investigator discretion.

For subjects developing any grade of diarrhea, loperamide (Imodium) is strongly recommended at the first onset of symptoms. Other antidiarrheal agents may be used if necessary.

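### The 4 mg antiemetic dexamethasone allowance in Protocol Section 9.3.2.2 makes no exception for acute pancreatitis, the one toxicity for which Table 5 orders an immediate permanent stop

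*Protocol*

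**What the plan says.** Protocol Section 9.3.2.2 has a sentence that begins "If dexamethasone dosing is permanently stopped due to toxicity in accordance with the dose modification guidelines described in" Table 5. It lets such a subject stay on oprozomib and pomalidomide. The very next sentence is the allowance: "Subjects may continue to take antiemetic doses of dexamethasone (4 mg) on days of oprozomib dosing, if tolerated, at the investigator's discretion". It carries two conditions, tolerance and discretion, and names no toxicity for which it is unavailable.

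Table 5 sets the action for each dexamethasone-related toxicity. For acute pancreatitis the entire entry is "Permanently discontinue dexamethasone". Other rows reach a permanent stop only after something milder has failed. For dyspepsia, ulcer or gastritis of Grade 3 or higher the row ends "If symptoms persist despite above measures, discontinue dexamethasone permanently", and for other nonhematologic toxicity it ends "If toxicity recurs despite 2 dose decrements, discontinue dexamethasone permanently".

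Elsewhere in Section 9.3.2.2, the rule on returning to a higher dose after a reduction does carry a toxicity exception. The subject may "be re-challenged with the dose level prior to the reduction at the start of the next cycle unless the subject experiences a GI hemorrhage".

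**The concern.** The allowance is written for people already stopped under Table 5, so on its face it reaches every stop reason in that table. For most rows this is coherent, because the table itself tries a lower dose before giving up and a small supportive dose is in the same spirit. For acute pancreatitis it is not, because the table recognises no lower dose at all.

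What is at stake is the safety of an individual subject. Section 6.2 plans about 20 sites. After a pancreatitis attributed to dexamethasone, each investigator would have to decide alone whether the permanent stop or the later permission applies. Demand for the antiemetic dose is realistic: Section 5.5.5 lists nausea and vomiting among the events seen in more than half of subjects.

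**Working it through.** The plan states no figure on this point, so the check compares Table 5 row by row with the allowance, and then looks for an exception elsewhere in the protocol.

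**Step 1. Table 5, all rows.**

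| Toxicity | First action | Lower dose tried | Permanent stop stated in the row |
|---|---|---|---|
| Dyspepsia, ulcer, gastritis, Grade 1–2 | Continue and treat | One level | No |
| Dyspepsia, ulcer, gastritis, Grade 3 or higher | Hold | One level | Yes, if it persists |
| Acute pancreatitis | Permanent stop | None | Yes, at once |
| Edema | Hold | Two levels | Yes, after the second |
| Confusion or mood change | Hold | Two levels | No |
| Muscle weakness | Hold | Two levels | Yes, if it persists |
| Hyperglycemia | Hold and treat | One level | No |
| Other nonhematologic | Hold | Two levels | Yes, after the second |

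Of 8 rows, 5 state a permanent stop: 3 after two reductions, 1 after one reduction, and 1 (acute pancreatitis) with no step before it.

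**Step 2. Size of the dose.** Oprozomib is given on 8 days per 28-day cycle (Section 9.2.1.1).

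- Allowance: 4 mg x 8 = 32 mg per cycle.
- Full dose on the 20 mg schedule: 20 x 8 = 160 mg, and 32/160 = 20%.
- Full dose on the 10 mg schedule (over 75 years): 10 x 8 = 80 mg, and 32/80 = 40%.
- Table 5 pancreatitis row: 0 mg.

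Table 4 also lists 4 mg as the second reduction level of the 10 mg schedule, so the antiemetic dose equals a treatment dose level in this protocol.

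**Step 3. Could an exception sit elsewhere?**

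- Section 9.4.3 (Pancreatitis) covers diagnostic work-up only and does not mention dexamethasone.
- Section 9.9 restricts glucocorticoids given on top of dexamethasone. It requires discussion with the medical monitor but does not address the 4 mg allowance, which has its own conditions.
- The dose-modification diagrams in Section 9.3.2.2 are not shown. Their title refers to oprozomib and pomalidomide, and the nonhematologic guidance points to Table 5 for dexamethasone. A dexamethasone exception there is unlikely but cannot be excluded.

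No text shown bars dexamethasone after pancreatitis.

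**The case against.** The best reply is that the existing text already gives the right answer. Table 5 is a specific, unqualified order and the allowance is a general permission, so the specific should govern. In addition, a subject with dexamethasone-attributed pancreatitis could hardly be said to tolerate the drug. A careful investigator may well read it that way. But the allowance is not free-standing. It follows directly on the sentence about Table 5 stops and is addressed to those subjects, so the rule of precedence does not settle the matter. Tolerance and discretion are judgement conditions on a permission. They let an investigator decline the dose, but they do not prohibit it.

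Second, the allowance applies only on oprozomib dosing days. If the unseen diagrams hold or stop oprozomib after pancreatitis, there may be no such days. This stands as a limit on the point.

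Third, the comparison with GI hemorrhage is imperfect. The exception in Section 9.3.2.2 concerns return to a higher dose, not a small supportive one. It shows only that the protocol writes toxicity exceptions where it wants them.

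A reader might go further and infer that ulcer or gastritis needs the same treatment, by analogy with Section 9.4.2: "Subjects who experience grade 1 or 2 GI hemorrhage may be re-challenged following discussion and agreement between the Amgen Medical Monitor and investigator". The documents do not support that. The agreement step there concerns oprozomib, the investigational product, and the ulcer and gastritis row itself accepts a lower-dose restart. A reader might also see Section 9.9 as a loophole, because emesis is among its examples. It already requires discussion with the medical monitor, which is a safeguard.

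**Conclusion.** The point holds as a narrow conflict between two instructions: a mandatory permanent stop for acute pancreatitis in Table 5, and a later permission in Section 9.3.2.2 that does not except it. It is a minor patient-safety matter and a cheap improvement.

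The possible exposure is up to 32 mg per cycle where the table allows none. How many subjects this could touch is unknown and may be zero. The documents give no count of dexamethasone stops by reason, and the Section 5.5.5 tables show no pancreatitis event. Increased lipase was a DLT in 2 of 39 OPomd subjects (Table 1), and a reader might take this as a sign of frequency. A raised lipase is not pancreatitis, and the table does not tie those events to dexamethasone, so no estimate can be built on it.

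A reader might also infer that the protocol directs re-exposure, or that the MTD is at risk. Neither follows. The text permits a dose and requires none, and no planned analysis is affected.

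The conclusion assumes that the diagrams not shown contain no dexamethasone exception and do not remove every oprozomib dosing day after pancreatitis.

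**What to change.** Add one clause to the allowance in Section 9.3.2.2: *except after a permanent stop for acute pancreatitis, when no further dexamethasone is given and non-steroid antiemetics are used.* A cross-reference in the Table 5 pancreatitis row is optional. Leave the allowance as it is for every other stop reason, and leave Section 9.9 unchanged.

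The cost is one clause in a protocol amendment. Endpoints, sample size, visits and analyses stay the same. A subject with this event loses one antiemetic option in a regimen with frequent nausea and vomiting. Section 9.4.2 still strongly recommends a 5-HT3 antagonist before each oprozomib dose and adds "Additional antiemetics may be used per investigator discretion".
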